11.5. Study Visits and Assessments

11.5.1. Open-label Baseline: Visit 1E (Day -1)

Subjects will be evaluated at the Open-label Baseline Visit to determine their eligibility to enroll in the study. The following study-related procedures will be performed at Open-label Baseline:

Confidential and Proprietary

- Obtain informed consent
- Review inclusion/exclusion criteria
- Demographics
- Administer EDE-Q modified (Subjects from Study SEP360-221 only)
- Dispense study drug (First dose taken the following day on Day 1)

Results for the following study-related procedures will be carried over from the core study Week 12 visit, and do not need to be performed for the Open-label Baseline visit:

- Physical and neurological examinations
- Vital signs, weight, and BMI
- ECG
- Scales: BE-CGI-S, SDS, SF-12 (Subjects from Study SEP360-221 only), C-SSRS, HAM-A, MADRS, and EDE-Q modified (Subjects from Study SEP360-321 only)
- Clinical laboratories (serum chemistry, lipid panel, hemoglobin A1c, hematology, urinalysis), UDS, and urine pregnancy test for females of child bearing potential
- Breath alcohol test

AEs and concomitant medications ongoing at the Week 12 visit in the core study will be carried over. Other data such as height will be carried over from other visits in the core study.

Further information on data carried over from the core study will be addressed in the DMP.

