15.3.1. Analysis Group

A total of 2 analysis groups will be formed based on a subject's previous participation in the core studies (ie, subjects previously randomized to dasotraline and subjects previously randomized to placebo). Group "All-Das" that combines these 2 analysis groups will be also presented. Summary tables, wherever applicable, will be presented by above analysis group, respectively.

- Pbo-Das: Subjects previously randomized to placebo in studies SEP360-221 or SEP360-321
- Das-Das: Subjects previously randomized to dasotraline group in studies SEP360-221 or SEP360-321

• All-Das: all subjects combined

Subjects continued from Study SEP360-221 will be further grouped into 2 analysis subgroups. In summary table they will be labeled as follows (ie, with one additional pooled group: 221-Das):

- Pbo-Das: previously randomized to placebo
- Das-Das: previously randomized to dasotraline 4–8 mg/day
- 221-Das: subjects continued from study SEP360-221

Subjects continued from Study SEP360-321 will be further grouped into 3 analysis subgroups. In summary table they will be labeled as follows (ie, with 2 additional pooled groups: All Das-Das and 321-Das):

- Pbo-Das: previously randomized to placebo
- Das4-Das: previously randomized to dasotraline 4 mg/day
- Das6-Das: previously randomized to dasotraline 6 mg/day
- All Das-Das: previously randomized to dasotraline (4 mg/day or 6 mg/day)
- 321-Das: subjects continued from study SEP360-321

Results will be presented by analysis subgroup as needed for limited analyses, wherever applicable.

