15.3.3.1. Adverse Events

All AEs will be coded using Medical Dictionary for Regulatory Activities (MedDRA) version 18.0 or higher.

Treatment-emergent adverse events (TEAEs) are those reported adverse events with onset data on or after the first day of the open-label treatment period through 7 days after study drug discontinuation (14 days for serious adverse events and deaths). The start of the open-label treatment period is defined as Day 1 for subjects previously randomized to placebo group and the OL Baseline visit date for subjects previously randomized to dasotraline groups.

A discontinuation-emergent adverse event (DEAE) is defined as an AE which has an onset after the last dose date of study drug through the Week 55 visit (ie, the last study visit in the withdrawal period).

Table summaries of AEs will be limited to TEAEs and DEAEs. All AE data will be displayed in data listings. For the sake of simplicity, hereafter TEAE is referred to as AE in this section.

The overall incidence (ie, number and percent of subjects with one or more AE in each category) of AEs, serious AEs, deaths, AEs leading to discontinuation, study drug-related AEs, study drug-related AEs leading to discontinuation, serious AEs leading to discontinuation, and serious study drug-related AEs, and serious study drug-related AEs leading to discontinuation will be summarized by analysis group.

The AEs also will be summarized by system organ class (SOC) and preferred term (PT) by presenting the number and percentage of subjects with each AE category. The incidence of AEs (by preferred term, grouped by SOC, and presented by analysis group) also will be summarized by severity, by the relationship to study medication, by the action taken regarding the study medication, as well as by the outcome.

The incidence of AEs of special interest, including but not limited to neuropsychiatric-related and cardiovascular-related AEs, will be summarized by analysis group. For time to the earliest onset of insomnia, Kaplan-Meier curves will be plotted by analysis group.

The overall incidence of DEAEs and serious DEAEs will be summarized by analysis group. The DEAEs also will be summarized by SOC and PT by presenting the number and percentage of subjects with each AE category.

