3.2. Randomization, Stratification and Blinding

This is an open-label extension study, therefore randomization and blinding is not employed.

322

4. Changes in Planned Analyses

There is not any change made in this SAP from the analyses planned in the protocol.

5. Effectiveness and Safety Variables

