6.1.11.3. Incomplete/Missing Dates

6.1.11.3.1. Start/End Dates for Adverse Event

Treatment-emergent adverse events (TEAEs) are those reported adverse events with an onset date on or after the first day of the open-label treatment period (See [Section 6.1.1.1](#) for definition of the OL treatment period), through 7 days after study drug discontinuation (14 days for serious adverse events and deaths).

A conservative approach will be used to handle the missing dates for AE onset date and end date to identify the treatment-emergent AE (ie, if the available incomplete date cannot determine treatment emergent status, the AE will be considered as a treatment-emergent AE). No imputation is to be done to calculate AE duration.

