7.4.2. Adverse Events

All AEs are coded using Medical Dictionary for Regulatory Activities (MedDRA) version 19.0 or higher.

Treatment-Emergent Adverse Event (TEAE)

Treatment-emergent adverse events (TEAEs) are those reported adverse events with onset data on or after the first day of the open-label treatment period through 7 days after study drug discontinuation (14 days for serious adverse events and deaths). The start of the open-label treatment period is defined as Day 1 for subjects previously randomized to placebo group and the OL Baseline visit date for subjects previously randomized to dasotraline groups.

AEs with a start date prior to the first day of the OL treatment period which are reported to have an increase in intensity, or which are reported to have a attribution in relationship to study medication (ie, attribution to possible related, probably related, related) after the first day of the OL treatment period are considered as TEAEs.

Discontinuation-emergent adverse events (DEAEs) are defined as AEs which have an onset after the last dose date of study drug through the Week 55 visit (ie, the last study visit in the withdrawal period).

Table summary of AEs will be limited to TEAEs and DEAEs. All AE data will be displayed in data listings. For the sake of simplicity, hereafter TEAE is referred to as AE.

The overall incidence (ie, number and percent of subjects with one or more AE in each category) of AEs, serious AEs, deaths, AEs leading to discontinuation, study drug-related AEs, study drug-related AEs leading to discontinuation, serious AEs leading to discontinuation, and serious

study drug-related AEs, and serious study drug-related AEs leading to discontinuation will be summarized by analysis group.

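### SAP 7.4.2 lets a related attribution alone turn an unchanged AE that began before the open-label period into a TEAE, a route absent from the protocol and not declared as a change

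*SAP*

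**What the plan says.** Protocol 15.3.3.1 defines the term by onset: "Treatment-emergent adverse events (TEAEs) are those reported adverse events with onset data on or after the first day of the open-label treatment period", with an upper limit of 7 days after discontinuation (14 days for serious AEs and deaths). SAP 6.1.11.3.1 does the same: "Treatment-emergent adverse events (TEAEs) are those reported adverse events with an onset date on or after the first day of the open-label treatment period".

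SAP 7.4.2 opens with that definition and then adds two routes for events that began earlier. The first is worsening: "AEs with a start date prior to the first day of the OL treatment period which are reported to have an increase in intensity, or". The second, joined to it by that final 'or', is attribution: "which are reported to have a attribution in relationship to study medication (ie, attribution to possible related, probably related, related) after the first day". The day in question is the start of the OL period.

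SAP Section 4 states: "There is not any change made in this SAP from the analyses planned in the protocol".

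Three other provisions decide what this does in practice:
- Protocol 11.5.1 brings earlier events into the extension: "AEs and concomitant medications ongoing at the Week 12 visit in the core study will be carried over".
- SAP 7.4.2 restricts the AE summary tables to TEAEs and discontinuation-emergent AEs.
- SAP 7.4.2 measures time to first treatment-emergent insomnia as the onset date minus the OL start date plus 1.

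The OL period starts on Day 1 for subjects who came from placebo and at the OL Baseline visit for those who came from dasotraline.

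**The concern.** Whether an event emerged on treatment should depend on when it began or worsened. The attribution route makes it depend on an opinion about cause, given for an event that may not have changed. Because the route admits earlier events only when they are rated related, its effect has one direction: it adds to the TEAE tables, and every event it adds is also a related TEAE.

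AE incidence is the first item under the primary objective. The effect is hardest to interpret in the group defined as "Pbo-Das: Subjects previously randomized to placebo in studies SEP360-221 or SEP360-321". There, an event that began before any dasotraline can appear as emerging on it. The three definitions also conflict: a TEAE flag programmed from SAP 6.1.11.3.1 would differ from one programmed from SAP 7.4.2, and the SAP does not tell the reader that it has departed from the protocol.

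**Working it through.** The documents state no AE rate or carry-over rate, so there is no figure of the plan's own to reproduce. The check compares the definitions, applies them to example records, and then illustrates size under stated assumptions.

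**1. Definitions compared**

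| Route to TEAE | Protocol 15.3.3.1 | SAP 6.1.11.3.1 | SAP 7.4.2 |
|---|---|---|---|
| Onset on or after first OL day | yes | yes | yes |
| Earlier onset, increased intensity | no | no | yes |
| Earlier onset, related attribution, no worsening | no | no | yes |

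**2. Example records.** All are ongoing at core Week 12 and unchanged in the extension.

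- *A, Pbo-Das.* Mild headache begins in core Week 6 on placebo and is rated possibly related in the extension. It is not a TEAE by onset or by worsening. It is a TEAE, and a related TEAE, under the attribution route.
- *B, Das-Das.* Dry mouth begins in core Week 3, is not rated related in the core study, and is newly rated probably related in the extension. It is a TEAE under the attribution route.
- *C, Das-Das.* The same dry mouth was already rated probably related in the core study. It is a TEAE only if 'attribution' includes an existing rating. The sentence does not settle this.
- *D.* The same dry mouth, rated unlikely throughout, is not a TEAE.

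B and D are the same event with the same course. Only the causality rating separates them.

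**3. Size.** Let p be the true new-onset incidence and q the share of the remaining subjects who bring in an unchanged earlier AE that the route admits. Both are assumptions.

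Reported incidence = p + (1 − p)q. Extra subjects = N(1 − p)q, with N = 500, the projected enrollment in protocol 7.1.

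| q | p = 5% | extra subjects | p = 15% | extra subjects |
|---|---|---|---|---|
| 1% | 5.95% | 4.8 | 15.85% | 4.3 |
| 3% | 7.85% | 14.2 | 17.55% | 12.7 |
| 5% | 9.75% | 23.8 | 19.25% | 21.3 |
| 10% | 14.50% | 47.5 | 23.50% | 42.5 |

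For example, 0.05 + 0.95 × 0.01 = 0.0595. With the route deleted, the reported figure returns to p in every row.

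**4. Insomnia Kaplan-Meier time.** With onset d days before OL start, the SAP formula gives −d + 1:
- d = 1 gives 0
- d = 7 gives −6
- d = 28 gives −27
- d = 84 gives −83

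None of these has a valid place on the time axis. Events admitted by worsening have the same problem if their original onset date is used. The AE-by-exposure tables have a similar gap: SAP 7.4.2 assigns an interval to TEAEs that start after the last dose but gives no rule for those that start before the first.

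**The case against.** The strongest reply is that the route will rarely operate. In protocol 12.3, each of the related categories requires that the event occurred within a reasonable time after study medication was given. A headache that began on placebo weeks before the extension fits none of them if study medication means open-label dasotraline. This makes such ratings less likely. It does not block them, because the SAP does not enforce the rule or say whether core or open-label drug is meant.

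A second reply is that the parallel with increased intensity points to a new attribution made during the extension. That is a fair reading, and record C is then not counted. Records A (if first rated related in the extension) and B still are. A reader might infer that core-study AEs in Das-Das are generally counted a second time. The documents do not support that: it holds for already-related events only under the wider reading, and these tables cover the extension alone.

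Third, the operation of the route depends on rules that the documents do not contain. Protocol 11.2.1 and 11.5.1 leave carry-over details to the Data Management Plan, and protocol 12.3 lists causality as an attribute of each AE without mentioning an attribution date. So it is not known whether carried-over AEs are re-rated. This limits any claim about frequency. It also means that the condition may be hard to program.

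Fourth, over-inclusion is conservative, the study is descriptive, and all AEs are listed. Those facts limit the harm. But describing incidence is the purpose of this study, and SAP 6.1.11.3.1 applies its conservative approach to missing dates, not to events with a known earlier onset.

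Finally, deletion has a real cost. Protocol 12.3 records frequency separately from severity, so an event that goes from intermittent to continuous and is newly judged related, with no higher severity grade, would leave the TEAE tables.

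**Conclusion.** The point holds as a matter of text. SAP 7.4.2 contains an undeclared TEAE route that needs no worsening and conflicts with protocol 15.3.3.1 and SAP 6.1.11.3.1. It can put unchanged placebo-onset events in Pbo-Das, and unchanged core-study events in Das-Das, into the primary AE incidence. In Das-Das this applies at least to events newly rated related in the extension. The direction is certain: counts can only rise.

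The size is unknown and may be small. A reader might take from the table that the incidence of a single preferred term could double or triple (9.75/5 = 1.95; 14.5/5 = 2.9). The documents do not support that. It needs 5% to 10% of subjects to carry in the same term. If, by assumption, total carry-over were 10% and one term held a fifth of it, 5% would become 0.05 + 0.95 × 0.02 = 6.9%. The formula also assumes the stated q among subjects with no new event. If carried-over events cluster in subjects who also have new ones, the increase is smaller.

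A reader might also see an error in the worsening route, because 'after' rather than 'on or after' could miss worsening on the first day. This is at most a one-day gap. Protocol 12.1.1 allows an exacerbation to be recorded as an AE in its own right, and such a record would meet the onset rule.

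**What to change.** - In SAP 7.4.2, delete the attribution route. A TEAE is then an AE with onset on or after the first OL day, or with earlier onset and an increase in intensity on or after that day. The existing upper time limits stay.
- Show AEs carried over without worsening, with their attribution, in a separate 'ongoing at OL entry' row or listing.
- For the insomnia Kaplan-Meier plot, either use the date of worsening for earlier-onset events or exclude subjects with insomnia ongoing at OL entry from the risk set. State which.
- Put the same definition in SAP 6.1.11.3.1, and declare the worsening route in SAP Section 4, since the protocol does not contain it.

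The cost is SAP wording, one flag in the AE dataset and one added row or listing. No new data are needed for the TEAE flag. Related-TEAE counts become slightly smaller, and an event newly judged related without worsening appears only in the separate row. No event is lost from view.

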5.3.2.2. Discontinuation-Emergent Signs and Symptoms (DESS) Scale

The DESS Scale is a clinician-rated instrument of 43 items used to evaluate signs and symptoms associated with discontinuation or interruption of monoamine reuptake inhibitor treatment. Each of the 43 signs and symptoms is assessed and placed in one of the following categories: new symptom, old symptom but worse, old symptom but improved, old symptom but unchanged, and symptom not present. Each sign and symptom that is placed in the category new symptom or in the category old symptom but worse receives 1 point. All other categories receive 0 points. The total DESS score is the sum of the number of points, which corresponds to the number of

symptoms rated as either a new symptom or as an old symptom but worse. The score ranges from 0 to 43, where higher scores indicate more discontinuation-emergent signs and symptoms.

The DESS is collected at Week 52/EOT, and Weeks 53, 54 and 55/EOS for subjects who enter the withdrawal period.

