The AEs also will be summarized by system organ class (SOC) and preferred term (PT) by presenting the number and percentage of subjects with each AE category. The incidence of AEs (by preferred term, grouped by SOC, and presented by analysis group) will also be summarized by severity, by the relationship to study medication, by the action taken regarding the study medication, as well as by the outcome. If a subject has the same AE on multiple occasions, the highest severity (severe, moderate, mild) recorded for the event and the highest drug relationship (unrelated, unlikely to be related, possibly related, probably related, and definitely related) will be presented, respectively. The relationship to study medication will be presented by 2 categories: related (which includes possibly related, probably related, and related, as determined by investigators), and not related (which includes unrelated and unlikely to be related, as determined by investigators). Furthermore, for AE summary by SOC and PT or by PT only, the following combined preferred terms will be summarized as well:

- Insomnia: Insomnia, Initial insomnia, Middle insomnia, Terminal insomnia
- Hallucination: Hallucination; Hallucination, auditory; Hallucination, gustatory; Hallucination, olfactory; Hallucination, synaesthetic; Hallucination, tactile; Hallucination, visual; Hallucinations, mixed; Hypnagogic hallucination; Hypnopompic hallucination; Somatic hallucination.

A Kaplan-Meier plot of the time to the first onset of treatment emergent insomnia (combined term) during the extension study will be presented by analysis group. Time to the first onset (in days) is defined as the earliest onset date of insomnia – start date of OL treatment period + 1. Subjects who do not experience any insomnia on or before the last dose date will be censored on the day of last dose.

Prevalence rate of insomnia (combined term) at a study day in the open-label treatment period is defined as number of subjects experiencing insomnia on the day divided by number of subjects remaining on open-label study treatment period at that time point. It is notable that subjects may experience multiple insomnia episodes during the study. Prevalence rate over time will be summarized and presented graphically by analysis group.

AE maximum relationship

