Each AE will be classified as ‘related’, ‘not related’, and ‘not specified’. TEAEs with a missing AE relationship will be classified as ‘not specified’. AE summary by the relationship to the study medication will be based on the highest relationship within an SOC and PT. Response values will be ranked in order from minimum to maximum as ‘not specified’ < ‘not related’ < ‘related’.

AE maximum severity

322

AEs with a missing severity will be classified as ‘not specified’. AE summary by the severity will be based on the maximum severity within an SOC and PT. Response severity values will be ranked in order from minimum to maximum as ‘not specified’ < ‘mild’ < ‘moderate’ < ‘severe’.

AE maximum action taken

AEs with a missing action taken will be classified as ‘unknown’. AE summary by the action taken will be based on the maximum action taken within an SOC and PT. Response action values will be ranked in order from minimum to maximum as ‘not applicable’ < ‘unknown’ < ‘dose increased’ < ‘unchanged’ < ‘dose reduced’ < ‘drug interrupted’ < ‘drug withdrawn’.

AE maximum outcome

AEs with a missing outcome will be classified as ‘unknown’. AE summary by the outcome will be based on the maximum outcome within an SOC and PT. Response outcome values will be ranked in order from minimum to maximum as ‘unknown’ < ‘recovered/resolved’ < ‘recovered/resolved with sequelae’ < ‘recovering/resolving’ < ‘not recovered/not resolved’ < ‘fatal’.

AEs of Special Interest (AESI)

A list of preferred terms that are to be combined for assessment of each of pre-specified adverse events category as below are provided in [Attachment 9.3](#).

- cardiovascular-related AEs
 - Cardiac arrhythmias
 - Vital signs-related
- metabolic-related AEs
 - Weight-related
 - Metabolic-Related (excluding weight)
- Neuropsychiatric-related AEs,
 - Neuropsychiatric AEs
 - Psychosis or Mania
 - Psychosis
 - Mania
- Combined insomnia
- Suicide and self-injury related AEs
- Spontaneous abortion /miscarriage (for female subjects only).
- Drug abuse and dependence (for AEs onset on/prior to the last study dose)
- Potential drug abuse (for AEs onset on/prior to the last study dose)
- Drug withdrawal related AEs (for AEs onset after the last study dose)

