- AEs by SOC and PT, Serious AEs by SOC and PT, and AEs leading to discontinuation by SOC and PT (sorted alphabetically by SOC and PT within SOC).
- AEs by PT, AEs with special interest by PT (sorted by descending order per frequency count)

Exposure categories to be summarized are given below:

- Exposure categories : 1-13 days, 14-27 days, 28-83 days, 84-167 days, \geq 168 days.

AEs by Subgroup

The TEAEs will be summarized by SOC, PT for subgroups (see [Section 6.1.12](#)) below:

322

- Age group at OL Baseline (years): < 40 years, ≥ 40 years
- Gender: Male, Female
- Race: White, Non-white
- BMI at OL Baseline: Non-obese , Obese class I/II, Obese class III

Discontinuation-Emergent Adverse Event (DEAE) (ie, AEs Onset After Last Study Dose)

All summary of DEAEs will be based on a ‘modified’ withdrawal population (see [Section 6.1.8](#)), which includes all subjects in the withdrawal population plus the subjects who do not enter withdrawal period, but their last study dose dates are at least 2 days earlier than their last study visit (ie, Week 52/EOT visit). The rationale of defining ‘modified’ withdrawal population is that the AE information after the last study dose is expected to be continuously collected till the last study visit

The overall incidence of DEAEs and serious DEAEs will be summarized by analysis group. The DEAEs also will be summarized by SOC and PT, and by PT of each analysis group.

In addition, incidence of DEAEs by SOC and PT will be also summarized using time intervals beginning with the earliest AE concurrent withdrawal duration in the withdrawal period, where denominators in percentage calculation for withdrawal duration intervals (in days) will be based on the number of subjects whose withdrawal duration are no less than the first day of the interval. Withdrawal duration (in days) will be derived as the last withdrawal visit date minus the last dose date +1 and withdrawal duration categories to be assessed are 1-7 days, 8-14 days, and ≥ 15 days.

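### The DEAE definition and the drug-withdrawal AESI category have no worsening clause, so an AE ongoing at the last dose that worsens afterwards drops out of the AE-based withdrawal tables unless the site enters it as a new AE

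*SAP*

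**What the plan says.** **DEAE.** The SAP (7.4.2) reads "Discontinuation-emergent adverse events (DEAEs) are defined as AEs which have an onset after the last dose date of study drug", and the end point is the Week 55 visit. The protocol (15.3.3.1) agrees: "A discontinuation-emergent adverse event (DEAE) is defined as an AE which has an onset after the last dose date of study drug". The SAP's later heading for the DEAE analyses repeats the limit: "ie, AEs Onset After Last Study Dose".

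**Drug-withdrawal AESI.** The SAP's list of special-interest categories has the same restriction: "Drug withdrawal related AEs (for AEs onset after the last study dose".

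**TEAE.** The window runs from the start of the open-label period to 7 days after the drug is stopped (14 days for serious events and deaths). The SAP adds a second route for "AEs with a start date prior to the first day of the OL treatment period which are reported to have an increase in intensity", or that come to be attributed to study drug, after the first open-label day. No last day is given for this route. The protocol's TEAE definition has no such route.

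**DESS.** SAP 5.3.2.2: "Each sign and symptom that is placed in the category new symptom or in the category old symptom but worse receives 1 point". SAP 7.4.6.2 tabulates new or worsened symptoms item by item, by visit and as worst case.

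**AE tables and recording.** SAP 7.4.2 puts only TEAEs and DEAEs into AE tables, while all AEs appear in listings. Severity tables take the maximum within system organ class and preferred term. Protocol 12.1.1 allows a flare-up of an existing condition to be an AE. Neither 12.1.1 nor 12.3 says whether a worsening opens a new record or updates the old one.

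**The concern.** Withdrawal effects are the first-listed secondary objective, and worsening of a symptom already present is one of the forms they can take. Symptoms ongoing at the last dose are foreseeable. Protocol 4.2 and 4.3 name insomnia among the most frequent AEs and as the main cause of AE discontinuation in the adult ADHD study, and AEs ongoing at Week 12 of the core study are carried over (11.5.1).

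The plan treats worsening as emergence in two places, the SAP's TEAE rule and the DESS, but not in the AE definitions built for the withdrawal period. If recording practice differs across the roughly 61 sites, DEAE incidence will partly reflect whether a site opens a new record or keeps the old one.

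**Working it through.** There is no figure to reproduce and no arithmetic behind the definition. The check applies the rules as written to three kinds of event.

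| Event | Kept as one record under its original start date | Worsening entered as a new AE after the last dose |
|---|---|---|
| (a) Starts after the last dose | DEAE; also a TEAE if onset is within 7 days (14 if serious) | Not applicable |
| (b) Starts on open-label drug, ongoing at the last dose, then worsens | Not a DEAE, not a drug-withdrawal AESI; remains a TEAE by onset | DEAE; also a TEAE if within 7 days (14 if serious) |
| (c) Starts before the open-label period, ongoing at the last dose, then worsens | Not a DEAE, not a drug-withdrawal AESI; can become a TEAE through the worsening clause | As (b) |

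**Step 1: the gap.** In (b) and (c), one-record handling removes the event from every DEAE and drug-withdrawal AESI table. New-record handling keeps it as a DEAE, and in the AESI if the term belongs there. The documents do not choose between the two. The wording of the TEAE clause, an AE with an earlier start date later reported as more intense, presupposes that at least some worsening AEs keep their original date.

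**Step 2: the open-ended TEAE clause.** The withdrawal period is nominally 385 − 364 = 21 days. A new non-serious AE stops being a TEAE after day 7 off drug, and a serious one after day 14. In case (c), worsening in the remaining 21 − 7 = 14 days (non-serious) or 21 − 14 = 7 days (serious) can still be booked as treatment-emergent, because the clause has no last day.

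**Step 3: severity.** In case (b), off-drug severity reaches the TEAE severity table only if the site updates the severity field of the existing record. The SAP's maximum-severity rule makes no cut at the last dose or at the end of the TEAE window, so nothing would stop it then.

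**Step 4: what remains visible.** In (b) and (c) the DESS can score the symptom if it is one of the 43 items and is rated worse. Changes from withdrawal baseline in CSSA, HAM-A and MADRS are also summarised, for totals and for individual scores (SAP 7.4.6.2).

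**Step 5: size.** The subjects missed would be the withdrawal-period N × the share with an AE ongoing at the last dose × the share of those that worsen × the share kept as one record × the share with no other DEAE (for the overall incidence). The documents give only a planned enrolment of about 500, and none of these five inputs.

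**The case against.** The strongest reply is that the withdrawal objective does not rest on DEAEs. Protocol 5.2 and 6.1 tie it to CSSA, DESS, HAM-A and MADRS, and those scales cover anxiety, depressed mood, irritability and sleep. This stands. A reader might infer that worsening on stopping is never counted as a withdrawal effect; the documents do not support that. What the scales do not supply is seriousness, relatedness, action taken and outcome, which protocol 12.3 requires for each AE. The SAP also built a modified withdrawal population (6.1.8) so that DEAE tables reach subjects who never enter the withdrawal period, for whom scheduled withdrawal scores will be sparse.

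Second, a site may enter an exacerbation as a new AE, and it is then a DEAE under the present text. This also stands, and it makes the omission conditional. It does not remove the problem, because the convention is unstated.

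Third, a reader might take "the highest severity (severe, moderate, mild) recorded for the event" to mean that off-drug severity is always reported as on-treatment severity. That sentence is conditioned on a subject having the same AE more than once. For a single continuing record, the transfer depends on the severity field being updated.

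Fourth, the TEAE clause is a limited precedent. It covers AEs that began before the open-label period, not those that start on open-label drug and worsen later. It shows that the SAP accepts worsening as emergence in principle, and no more.

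**Conclusion.** The point holds within limits. The DEAE definition and the drug-withdrawal AESI category are onset-only in the current text. An AE ongoing at the last dose that worsens afterwards is left out of the AE-based withdrawal tables unless the site enters a new AE. This is inconsistent with the SAP's own TEAE clause and with DESS scoring. Separately, the TEAE worsening clause lacks an end date and can label late off-drug worsening as treatment-emergent.

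The loss is confined to the AE tables. A reader might want to attach a percentage to it, but every input would have to be assumed, so none is given. No hypothesis test is affected, because all analyses are descriptive. The conclusion assumes that at least some worsening events are kept under their original start date. CRF completion instructions, which are not among the documents, could settle how often that happens.

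**What to change.** 1. Define a DEAE, and the drug-withdrawal AESI, as an AE with onset after the last dose, or an AE ongoing at the last dose that is reported to increase in intensity after it, in both cases through the Week 55 visit.
2. Show new-onset and worsened events in separate rows, so that the onset-only incidence remains readable.
3. End the TEAE worsening clause on the same day as the TEAE window (7 days after the last dose, 14 for serious events and deaths). Where severity changes are dated, limit the TEAE severity table to severity recorded within that window.
4. State how a change in severity is recorded and dated: on the existing record or as a new one.
5. Declare the change in SAP Section 4. That section now reports no departure from the protocol, although the SAP's TEAE worsening clause is already absent from the protocol's definition.

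The cost is revised SAP wording and a small extra derivation. The derivation needs severity changes to be dated relative to the last dose, or entered as new records. The existing TEAE clause needs only a change after the first open-label day, so the available data must be checked before database lock. If neither form was collected, the onset-only limit should be stated in the table footnotes and the study report. DEAE incidence may be slightly higher under the wider definition.
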